In light of these data, the aim of the current study is to test the efficacy of a fully online, Instagram-based intervention designed to reduce heavy alcohol use among young adults. Participants will be randomly assigned to either an intervention or an assessment-only control condition. Analyses will compare mean changes in past-month alcohol use, alcohol-related consequences, mindfulness, and use protective behavioral strategies in intervention versus control group participants at 10-week follow-up. Secondary analyses will assess the perceived acceptability of the intervention and its posts, as well as the degree to which the posts were seen and remembered by participants. It is hypothesized that (1) participants in the intervention group will show greater decreases in alcohol use and consequences and greater increases in mindfulness and protective behavioral strategy use than participants in the control group and (2) intervention posts will be remembered and given high acceptability ratings.

Pilot Work

The proposed project will build on a pilot study conducted by the PI between April 2021 and December 2021. During this pilot study, 50 Wayne State University students between the ages of 18-28, who reported regular binge drinking, were given an Instagram-based alcohol intervention (developed specifically for the study by the PI). After an initial orientation session, participants were asked to follow the study Instagram page and were then shown intervention posts each day for 6 weeks. A subset of participants was also exposed to a series of Instagram ‘stories’

(i.e., images that are available for viewing for twenty-four hours after posting), which were posted once every two days. Instagram content consisted of mindfulness exercises, presentation of drinking norms, information about protective behavioral strategies, and specific affirmations (described in more detail below).

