In order to prevent delays between baseline survey completion and the start of the Instagram intervention, subgroups of participants may be randomized to condition and exposed to the intervention in different data collection waves. Each wave will last for six weeks and will contain a total of forty-two Instagram posts and twenty-one Instagram ‘stories’ (i.e., images that are available for viewing for twenty-four hours after posting and can utilize mechanics like polls and quizzes). Intervention content will be posted once per day throughout the 6-week intervention period, alternating between posting times of approximately 8 AM EST/EDT and 8 PM EST/EDT, and intervention ‘stories’ will be posted once every two days.

10-Week Follow-Up Survey. Ten weeks after the intervention start date (and four weeks after the end of the intervention), participants will be emailed a follow-up survey, which will contain the same questionnaires as the baseline survey. Participants in the intervention condition will also be asked to rate how relevant, respectful, helpful, empathic, personalized, and interesting they felt the intervention content had been, using 5-point Likert scales. Additionally, participants in the intervention group will be shown specific examples of previously posted content and asked to rate each specific post on the dimensions listed above, as well as to indicate whether they remembered seeing those particular posts.

The follow-up survey will remain open for two weeks, and reminder messages will be sent during this time to encourage participant completion. Each participant will receive \$10 for completing the baseline session and \$15 for completing the 10-week online follow-up survey.

Analytic Strategy and Hypotheses

The data will be assessed for normality, missing data, and outliers. Data transformation, multiple imputation, and list-wise deletion will be utilized as needed. Mixed repeated-measure ANOVAs will be used to analyze within- and between-group differences in participants' alcohol consumption, alcohol-related consequences, mindfulness practices, and use of protective behavioral strategies at baseline and 10-week follow-up. Average acceptability ratings will be calculated using group means.

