We predict that (1) intervention participants will show greater decreases than control group participants in past-month quantity and frequency of alcohol use, binge-drinking episodes, and alcohol-related consequences, and (2) intervention participants will show greater increases than control group participants in the use of protective behavioral strategies and mindfulness practices. We also predict that the intervention as a whole, and specific intervention posts will be remembered and rated as highly acceptable across several dimensions (i.e., relevant, respectful, helpful, empathic, personalized, and interesting).

Figures

Figure 1. Standardized Drink Infographic

Figure 2. Example of TLFB Calendar

**12 fl oz of
regular beer**

=

**8–9 fl oz of
malt liquor
(shown in a
12 oz glass)**

about 5%
alcohol

about 7%
alcohol

**5 fl oz of
table wine**

=

about 12%
alcohol

**1.5 fl oz shot of
80-proof spirits
(whiskey, gin, rum,
vodka, tequila, etc.)**

about 40%
alcohol

The percent of “pure” alcohol, expressed here as alcohol by volume (alc/vol), varies by beverage.

December 2022

Sunday	Monday	Tuesday	Wednesday	Thursday	Friday	Saturday
				1	2	3
4	5	6	7	8	9	10
11	12	13	14	15	16	17
18 Hanukkah Begins	19	20	21 Winter Solstice	22	23	24 Christmas Eve
25 Christmas Day	26 Hanukkah Ends / Boxing Day	27	28	29	30	31

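### The 10-week recall item covers only posts that were really shown, so the secondary claim that posts are remembered cannot be separated from false recognition; a few unposted foils would fix this cheaply

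*Combined protocol and SAP*

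**What the plan says.** The 10-Week Follow-Up Survey paragraph (Chapter 2: Methods, Procedure) states that "participants in the intervention group will be shown specific examples of previously posted content", to be rated on six dimensions, "as well as to indicate whether they remembered seeing those particular posts". The recall question is given to the intervention arm only.

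The aims, at the end of the Instagram Interventions section, list among the secondary analyses "the degree to which the posts were seen and remembered by participants". The second hypothesis there is that "intervention posts will be remembered and given high acceptability ratings". Analytic Strategy and Hypotheses repeats the prediction: "specific intervention posts will be remembered and rated as highly acceptable across several dimensions".

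For the analysis of these items that section says only: "Average acceptability ratings will be calculated using group means". It gives no summary, comparator or threshold for recall.

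**The concern.** A recognition question is interpretable when some items are known not to have been shown. The yes-rate on those items shows how often people claim to remember something they cannot have seen. This plan has no such items and no unexposed group answering the question, so neither arm supplies a false-recognition rate.

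The documents give three reasons to expect some false yes answers:

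- Under Recruitment and Baseline, participants agree to follow the page and to like posts to show that they have seen them. A no may then feel like admitting a lapse.
- The question comes four weeks after the last post and ten weeks after the first, over 42 posts and 21 stories.
- Affirmation posts are deliberately generic, and some captions in the Appendix are close to one another: 7 and 21 both ask about next week's goals. Familiarity with a theme can pass for memory of a particular post.

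At stake is how the second hypothesis is read, and any use of the recall figure as evidence that the content reached participants.

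**Working it through.** The plan states no expected recall rate, threshold or power for recall, so there is no figure to reproduce. The calculations below only illustrate the point.

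**Inputs from the documents:** 40 participants in the intervention arm (Participants section); recall asked of that arm only, on posted content only. The number of example posts is not stated.

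**Assumed inputs:** true recognition r; yes-bias g, the chance of answering yes without remembering; 32 completers of 40 (80%); within-person correlation of foil answers of 0 or 0.3.

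**1. Expected yes-rate.** y = r + (1 - r)g.

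| r | g = 20% | g = 40% |
|---|---|---|
| 30% | 0.30 + 0.70 × 0.20 = 44% | 0.30 + 0.70 × 0.40 = 58% |
| 50% | 0.50 + 0.50 × 0.20 = 60% | 0.50 + 0.50 × 0.40 = 70% |

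With r = 30%, a majority of yes answers needs g above (0.50 - 0.30)/0.70 = 29%.

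**2. What a given yes-rate would mean.** r = (y - g)/(1 - g). For an observed 80% yes:

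| g | implied r |
|---|---|
| 0% | 80% |
| 20% | 75% |
| 40% | 67% |
| 60% | 50% |
| 80% | 0% |

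The yes-rate alone gives an upper limit for r and nothing more.

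**3. Compared with sampling error.** For one post and n = 40, the 95% half-width is 1.96 × √(0.8 × 0.2/40) = 12 points at 80% yes, and 1.96 × √(0.7 × 0.3/40) = 14 points at 70%. The range in step 2 is wider than this, and a larger sample would not narrow it.

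**4. What four foils would give.** For a false-alarm rate of 30% and 32 completers:

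- independent answers: √(0.3 × 0.7/(32 × 4)) = 4.1 points;
- within-person correlation 0.3: design effect 1 + 3 × 0.3 = 1.9, so 4.1 × √1.9 = 5.6 points.

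If all 40 complete, the same formulas give √(0.21/160) = 3.6 and 5.0 points. These cover sampling of participants only, not variation among foils.

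**5. What the difference measures.** If foils draw yes answers at the same rate g, hit rate minus false-alarm rate is y - g = r(1 - g). With r = 30% this is 24 points at g = 20% and 18 points at g = 40%. The difference is zero when nothing is recognized, and otherwise does not exceed r.

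**The case against.** The strongest reply is that this is a secondary, descriptive item on which no test or decision rests, and that honest labelling removes most of the risk. That stands, and it limits the weight of the point.

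A reader might infer that yes is the correct answer to every item. The documents do not support this. The question is about having seen the post. Eligibility requires Instagram use only two to three times a week, while posts appear daily and stories last 24 hours, so a truthful no is possible. What is missing is any item that was certainly not shown.

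A reader might also infer that the hypothesis cannot fail, or that the figure is certain to be inflated. Neither follows. A yes-bias of zero is not excluded, and r = 30% with g = 20% gives 44%, short of a majority. Whether the hypothesis can fail also depends on a success criterion, which the plan does not state.

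Likes offer a partial check, because participants supply their usernames and liked and unliked posts could be compared within person. But likes record exposure, are an agreed task, and may be given without reading. The plan does not link them to recall.

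The text does not rule foils out, but it defines the items as previously posted content. Foils do bring a design problem: each real post is to be rated as well as recalled, so a foil with only a yes/no question would stand out. This affects how the foils are placed and does not remove the case for them.

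**Conclusion.** The point holds as a cheap improvement to one secondary hypothesis. As designed, the yes-rate may overstate recognition, and the trial cannot say by how much. The illustrative 44-58% for true recognition of 30% rests wholly on assumed values of r and g and on a simple guessing model. The structural finding does not: with only posted content shown and only exposed participants asked, there is no false-alarm rate to subtract. The between-arm comparisons of drinking, consequences, protective strategies and mindfulness are unaffected.

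**What to change.** Before the follow-up survey is fielded, add a recognition block for the intervention arm, placed after all drinking, consequences, protective-strategy and mindfulness measures and before the post ratings.

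- Mix the real example posts with about four never-posted foils in the same style, in random order, with an instruction that some may not have been shown.
- Ask only the yes/no recognition question in this block. Then collect the six ratings on the real posts only, so that the format does not reveal the foils.
- Report the hit rate, the false-alarm rate and their within-person difference with a confidence interval. Base the conclusion that posts were remembered on the size of that difference and its interval, not merely on hits exceeding false alarms.

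The cost is about four images, four extra yes/no items and one instruction; the recall questions on real posts are moved, not added. The survey becomes slightly longer, and the recall figure will probably look less favourable. A false-alarm rate that was not measured cannot be recovered by later analysis.

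If foils are not added, report the result as self-reported recall, compare recall of liked and unliked posts within person as a partial check, and do not present the hypothesis as confirmed.

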Past Month Alcohol Use will be assessed with The Timeline Follow-Back (TLFB; Sobell & Sobell, 1996), a highly reliable interview that uses a calendar and multiple procedures to aid in the retrospective reporting of substance use. During the TLFB, participants are asked to report how many standard drinks they consumed each day, during the past 30 days. Before beginning the task, participants will be provided with a graphic that illustrates the size of a standard drink (Figure 1), as well as a calendar marked with major holidays (Figure 2). The online version of the TLFB has been found to be a reliable measure of alcohol use in young adult samples (Rueger et al., 2012).

Past-Month Alcohol Consequences will be assessed using the Brief Young Adult Alcohol Consequences Questionnaire (BYAACQ; Kahler et al., 2005), a well-validated 24-item questionnaire designed to assess high- and low-level drinking consequences commonly experienced by young adults. The BYAACQ has shown good validity among young adults and is

designed to be sensitive enough to detect drinking consequences within non-clinical samples (Stamates, Yang, & Lau-Barraco, 2022).

Protective Drinking Practices will be assessed with the Protective Drinking Practices Scale (PBS; Martin et al., 2020), a 20-item questionnaire which measures the frequency of protective behavioral strategy use in the past month (e.g., “Limited cash before going out” rated on a Likert scale ranging from ‘Never’ to ‘Always’). This measure has shown good validity for use among young adults in the United States (Jordan et al., 2021).

Mindfulness Practices will be assessed using the Mindful Attention Awareness Scale (MAAS; Brown & Ryan, 2003). The MAAS is a 15-item questionnaire that assesses the frequency of engaging in mindfulness and mindfulness-related practices (e.g., “I find it difficult to stay focused on what’s happening in the present” rated on a Likert scale ranging from ‘Almost Always’ to ‘Almost Never’). The MAAS has been well-validated in young adult populations (MacKillop & Anderson, 2007).

Intervention Acceptability will be assessed using six domains of acceptability (i.e., relevant, respectful, helpful, empathic, personalized, and interesting). A selection of individual posts will be rated, in addition to the overall intervention. Ratings will be made using single-item, 5-point Likert scales.

Intervention Content

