prioritize the things that matter to you and to achieve your goals! Put your values first, and the rest will follow”) or prompt participants to reflect on their own individual values and skills (e.g., “You did that! Give yourself credit where credit is due. Think about your goals and go for them!”).

Protective Behavioral Strategies. Protective behavioral strategy posts will reference specific behaviors that can increase or decrease the consequences of alcohol use (e.g., “Drinking games can be dangerous. Drinking too much, especially in short spans, can lead to alcohol poisoning. What was once fun can become frightening.”). Other posts will ask participants to reflect on protective behavioral strategies that they have used in the past or have seen others use effectively.

Procedure

Recruitment and Baseline. Eighty participants will be recruited using a screening survey administered through Prolific, a research recruitment website. Eligible participants will be given access to the main study on Prolific, and those randomized to the intervention condition will be invited to follow the study Instagram page. Before being given the Instagram page username, participants will be asked to agree to the following study guidelines/expectations:

- 1) They will follow the Instagram intervention page for the duration of the 6-week study
- 2) They will treat their fellow group members with respect and avoid “trolling” (i.e., contacting other participants, posting disrespectful comments, using obscene language, etc.)
- 3) They will participate, comment, and share when they feel comfortable doing so
- 4) They will ‘like’ intervention content posts as they appear on their feed (as a way of indicating that they have seen them)

5) While their comments and interactions on the page will not be seen by the general public, other participants will be able to view them and interact with them

After agreeing to these expectations, participants will be asked to provide their Instagram username, sent a baseline survey containing a link to the Instagram page and the baseline questionnaires, and instructed to begin following the Instagram page immediately.

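### Who stays in the between-arm comparison is settled after the data are seen, and the planned ANOVA compares change scores where baseline adjustment would be more precise

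*Combined protocol and SAP*

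**What the plan says.** In the combined protocol and SAP, Analytic Strategy and Hypotheses, the handling of missing data, outliers and non-normality takes two sentences. The first is "The data will be assessed for normality, missing data, and outliers" and the second is "Data transformation, multiple imputation, and list-wise deletion will be utilized as needed". The method follows: "Mixed repeated-measure ANOVAs will be used to analyze within- and between-group differences", for each outcome at baseline and week 10. No trigger, order of steps, imputation model, outlier definition or sensitivity analysis is given.

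The study aim, at the end of Instagram Interventions, fixes the target: "Analyses will compare mean changes in past-month alcohol use" and the other outcomes, intervention against control. Arms are compared as randomized, so assignment to arm is not in doubt. No section says that all randomized participants are analysed.

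Two parts of Procedure bear on who might be missing:

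- **Recruitment and Baseline**, for the intervention arm: "Before being given the Instagram page username, participants will be asked to agree to the following study guidelines/expectations". Only after agreeing and giving a username are they "sent a baseline survey containing a link to the Instagram page and the baseline questionnaires". No such step is described for controls.
- **10-Week Follow-Up Survey**: the survey stays open for two weeks, "reminder messages will be sent during this time to encourage participant completion", and each participant receives $15 for completing it.

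**The concern.** A mixed ANOVA with two time points needs both values from each participant. Unless missing week-10 values are imputed, anyone without the follow-up survey leaves the comparison. The plan leaves that choice open until the data have been inspected.

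Two things are at stake. If loss is related to drinking and differs between arms, the difference among completers can be wrong in either direction. Some difference in loss is plausible, because only intervention participants face the agreement step and the extra content ratings at follow-up, but nothing in the documents shows that it will occur.

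Separately, the arm-by-time test uses the baseline value only by subtracting it. A regression on the baseline value uses the same data more efficiently and protects against one form of selective loss.

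**Working it through.** **The plan's own figures.** There is none to reproduce here: the documents give no dropout rate, SD, distribution or baseline-to-follow-up correlation. From the documents come 40 per arm, two time points, and drinking recorded as daily drinks ("participants are asked to report how many standard drinks they consumed each day, during the past 30 days"). Everything else below is assumed.

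**Assumed inputs.** Poisson counts around a lognormal mean, latent correlation 0.7, and a 20% proportional reduction in the intervention arm. There are four scenarios: A mean 40, CV² 1; B mean 40, CV² 0.5; C mean 6, CV² 1; D mean 6, CV² 0.5. The standard errors of the difference in change at 40 per arm are 7.7, 5.4, 1.35 and 1.07.

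**Step 1: what the ANOVA tests.** With two arms and two times, the arm-by-time interaction is the two-sample comparison of (week 10 − baseline).

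**Step 2: precision.** Take A.

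- Variance of a count: 40² × 1 + 40 = 1640. At week 10 in the intervention arm: 0.64 × 1600 + 32 = 1056.
- Covariance: 1600 × (2^0.7 − 1) = 999 in controls; 0.8 × 999 = 799 in the intervention arm.
- Change scores: 2(1640 − 999) + (1640 + 1056 − 2 × 799) = 1282 + 1098 = 2380, so SE = √(2380/40) = 7.71.
- Baseline-adjusted: common slope (999 + 799)/(2 × 1640) = 0.548. Residual variances are 1640 − 2 × 0.548 × 999 + 0.548² × 1640 = 1038 and 1056 − 2 × 0.548 × 799 + 0.548² × 1640 = 673. SE = √(1711/40) = 6.54.
- Ratio 6.54/7.71 = 0.85, about 15% narrower.

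Simulated at 40 per arm across the four scenarios, intervals were 16–19% narrower, with power 19–42% against 14–33% and type I error 4–5%.

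Part of this gain comes from the assumed effect shrinking the week-10 variance. With equal variances the large-sample SE ratio is √((1 + ρ)/2), where ρ is the correlation of the observed values. That is 19% narrower at ρ = 0.3, 13% at 0.5, 8% at 0.7 and 5% at 0.8. The gain is always positive but depends on ρ.

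**Step 3: selective loss in the intervention arm only.** Control loss is 10% at random. Intervention loss is 30% above and 10% below the arm's median, about 20% overall. Differences in drinks, with error relative to full data:

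| Loss depends on | Scenario | Full data | Completers, change | Completers, baseline-adjusted |
|---|---|---|---|---|
| Baseline drinking | A | −7.97 | −6.69 (−16%) | −8.05 (+1%) |
| | B | −8.06 | −6.94 (−14%) | −8.00 (−1%) |
| | C | −1.19 | −0.93 (−22%) | −1.20 (+1%) |
| | D | −1.21 | −0.94 (−22%) | −1.19 (−2%) |
| Follow-up drinking | A | −8.01 | −8.31 (+4%) | −9.31 (+16%) |
| | B | −8.04 | −8.38 (+4%) | −9.08 (+13%) |
| | C | −1.19 | −1.32 (+11%) | −1.47 (+24%) |
| | D | −1.19 | −1.34 (+13%) | −1.46 (+23%) |

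If lighter drinkers are lost instead, the signs reverse. Baseline-related loss then puts completers off by +14 to +23%, with adjustment within 2%. Follow-up-related loss puts completers off by −4 to −13% and adjustment by −14 to −23%. Imputing from arm and baseline agreed with baseline adjustment to within 0.7 percentage points of the effect throughout.

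Against sampling error, A's first row is (7.97 − 6.69)/7.7 = 0.17 SE. The largest shift anywhere is 0.26 SE.

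**Step 4: the same mechanism in both arms.** Completers are off by about 3–7% when loss depends on baseline drinking and 5–8% when it depends on follow-up drinking. Adjustment does not remove the baseline-related shift: the assumed effect is proportional, so heavier drinkers carry more of it.

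**Step 5: the proposed rule at 40 per arm, baseline-related loss, 20 imputations.** Mean interval widths against completers-only change are 26.3 v 31.1, 19.7 v 22.9, 4.66 v 5.65 and 3.79 v 4.55, which is 14.0–17.5% narrower. Baseline-adjusted completers without imputation gave 26.0, 19.4, 4.61 and 3.75. The gain therefore comes from the adjustment; imputation costs about 1% in width. Type I error was 4.4–4.7%.

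**The case against.** The strongest reply is that the sentence already names multiple imputation and transformation, the tools that keep non-responders and extreme values in. That is right: the gap is the absence of a commitment, not the absence of a method.

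Three stronger readings are tempting, and the documents do not support them.

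- **Outliers will be deleted.** The plan says they will be assessed. List-wise deletion ordinarily refers to missing values, and its link to outliers would be inferred only from the order of two sentences.
- **A favourable analysis will be picked.** The open wording leaves room for that, but nothing says or suggests it will be done.
- **Loss will differ by arm.** The agreement step makes it possible. Against it stand reminders, a two-week window and the same payment for both arms, and no attrition figure is given.

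Two technical objections also stand. The 14–23% error requires drinking-related loss in one arm only. And imputation from baseline is not uniformly better: when intervention-arm loss depends on follow-up drinking it is off by 13–24%, against 4–13% for completers.

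The agreement step also falls before the baseline survey, whereas the calculations model loss at week 10 with baseline observed. People lost at that earlier point cannot be imputed from baseline under any rule proposed here.

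**Conclusion.** The point holds and should be acted on, in a limited form. The plan does not commit to keeping randomized participants without a 10-week survey in the comparison, and it leaves that choice until after the data are inspected. This rests on the text alone and is secure.

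The size of any bias is not secure. It is 14–23% of a 20% effect under one-arm, baseline-related loss and about 3–7% when both arms lose participants in the same way. It is never more than 0.26 SE, and near nil if loss is unrelated to change.

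The firmer gain is precision: replacing the change-score test by baseline adjustment narrows intervals by about 16–19% under the assumed latent correlation of 0.7 and 20% effect, by an amount that varies with the true correlation. It needs no data beyond those already planned.

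**What to change.** Replace the sentence with one stated primary rule:

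- For each outcome, the primary between-arm test is a linear model of the 10-week value on arm and baseline value, on the original scale and in assigned arms. This keeps the mean-change target of the study aim. Within-group change can still be reported descriptively.
- Every randomized participant with baseline data is included. Missing 10-week values are multiply imputed from arm and baseline measures. List-wise deletion is not used for the primary analysis.
- Extreme but possible values stay in. Only impossible entries (negative or non-numeric drinks, scores outside the scale) are set to missing, blind to arm. Any ceiling on daily drinks is fixed before data are seen.
- Sensitivity analyses: complete-case; log(x+1) for drinking counts only; and a delta analysis that shifts imputed intervention values both ways. For drinking counts the shift runs up to 30%, since undoing the follow-up-related error in Step 3 took shifts of 15–30%. For bounded scores it stays within the scale range. The delta analysis is needed because imputation from baseline does not correct, and can worsen, this kind of bias.
- Report loss by arm. Anyone randomized who leaves before the baseline survey is counted separately and stated as excluded.

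The cost is a few lines of text and a little more analysis with standard software. The original scale also gives up some power for skewed counts: 18.9, 34.1 and 16.3% in scenarios A to C against 26.5, 39.3 and 19.1% on log(x+1), with no loss in D (22.5 v 21.4%).

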The intervention was rated as highly acceptable. Additionally, analyses revealed significant within-subjects decreases in past-month alcohol consumption, drinking days, and binge-drinking days post-intervention; however, there were no significant changes in past-month protective behavioral strategies and mindfulness practices. Although this pilot study provided critical feedback about intervention development and administration, it was intentionally small and did not include a control group, thereby limiting the interpretation of findings. The proposed study builds on this pilot work by replicating the study with a larger sample size, a community-based sample, and an assessment-only control group. Specific procedures are described below.

Chapter 2: Methods

Participants

Eighty participants will be recruited from Prolific, an online platform designed to screen and recruit potential research participants for online studies. Power analyses indicate that, with an N of 80 (two groups of 40), this study will be sufficiently powered to detect effect sizes of .20, an effect size consistent with other standalone, technology-delivered, cognitive behavioral interventions for alcohol use (Kiluk et al., 2019).

In order to be eligible for the study, participants must: (1) be a US resident, (2) be between the ages of 18 and 30; (3) report at least two binge-drinking episodes (i.e., four or more drinks in one sitting for cis women, five or more drinks in one sitting for cis men or transgender and

nonbinary individuals) per month over the past three months; (4) have an active Instagram page; and (5) report regular Instagram use (i.e., at least 2-3 times a week).

Participants will be randomized to either an intervention condition in which they will follow an Instagram page and engage with content during the six-week study period or to an assessment-only control condition in which they will be emailed assessment measures, but will not be exposed to intervention content.

Measures

Demographics will be assessed at baseline. Participants will be asked to answer questions about their sex, gender, age, race, ethnicity, sexual orientation, education level, and household income. State of residence will also be assessed.

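### The effect scale for the drinking and consequence outcomes is left open: an unspecified transformation, triggered by a normality check, can replace the stated comparison of mean changes and alter the verdict

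*Combined protocol and SAP*

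**What the plan says.** The paragraph of aims that closes the introduction, before Pilot Work, states the target: "Analyses will compare mean changes in past-month alcohol use", with consequences, mindfulness and protective strategies listed alongside, intervention against control at 10 weeks.

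Under Measures, alcohol use comes from the Timeline Follow-Back: "participants are asked to report how many standard drinks they consumed each day, during the past 30 days". Consequences come from a 24-item questionnaire.

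Analytic Strategy and Hypotheses begins "The data will be assessed for normality, missing data, and outliers", continues "Data transformation, multiple imputation, and list-wise deletion will be utilized as needed", and then gives the model: "Mixed repeated-measure ANOVAs will be used to analyze within- and between-group differences", at baseline and 10 weeks. The hypothesis is that "intervention participants will show greater decreases than control group participants in past-month quantity and frequency of alcohol use", and likewise for binge episodes and consequences. Whether the decrease is absolute or proportional is not said.

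No section names a transformation, the finding that would trigger it, the outcomes it could apply to, the handling of zero counts, the scale for reporting, or a companion analysis on the untransformed scale.

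**The concern.** Four of the six predicted measures (quantity, frequency, binge episodes, consequences) are counts or count-like totals. Such data are usually right-skewed, so a normality check is likely to fail and a transformation is a foreseeable branch of the plan.

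With two time points, the group-by-time term is a two-sample t-test on change scores. On raw data it compares mean changes, as the aim says. After a nonlinear transformation it compares something else. The quantity tested, and possibly the conclusion, would then depend on an unspecified step taken after the outcome data are in hand.

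**Working it through.** **Inputs from the documents.** 80 participants, two groups of 40 (Participants); two time points; the outcomes above. The one design figure is the claim that "this study will be sufficiently powered to detect effect sizes of .20". It states neither the metric nor the scale, and this point does not rest on it. The documents give no means, SDs, correlations, alpha or dropout, so everything simulated below is assumed (two-sided 0.05, no dropout).

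**1. What the interaction term tests.** Let b and f be baseline and 10-week values, with subscript 1 for intervention and 0 for control.
- Raw: D = (mean f₁ − mean b₁) − (mean f₀ − mean b₀), the difference in mean change.
- Log: exp(D) = (GM f₁ / GM b₁) ÷ (GM f₀ / GM b₀), where GM is the geometric mean. With log(x+1), needed if there are zeros, this holds approximately.
- Square root: neither a difference in means nor a ratio.

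**2. Can the scales disagree?** Assumed typical values:
- Intervention 50 to 38, control 30 to 21. Raw: −12 − (−9) = −3 drinks, favouring intervention. Log: 38/50 = 0.76 and 21/30 = 0.70; 0.76/0.70 = 1.086, favouring control. Square root: −0.012, practically nothing.
- A 25% fall in each arm, from 50 and from 40: −12.5 against −10, so 2.5 drinks on the raw scale and zero on the log scale.
- Equal baselines, 40 to 30 against 40 to 35: raw −5, square root −0.44, log −0.154 (ratio 0.857). All agree.
- Identical baselines (10, 20, 40, 90) with an uneven response, to 5, 12, 36, 90 against 10, 18, 36, 70: raw +2.25 favours control; square root −0.146 and log −0.212 favour intervention.

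So disagreement needs chance baseline imbalance or an effect that varies with drinking level. For imbalance, the SE of the difference in log means is s × √(2/40) = 0.224s. A 50:40 ratio in either direction (ln 1.25 = 0.223) has probability about 10%, 21% or 32% for s = 0.6, 0.8 or 1.0. The 50:30 ratio of the first example (ln 1.667 = 0.511) is much rarer: even at s = 1.0, 0.511/0.224 = 2.28, about 2%.

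**3. How often at 40 per arm?** Poisson-lognormal counts, median 30 drinks, correlation 0.6, common 20% fall, 20,000 trials per setting; ranges are over log-SD 0.6 to 1.0:

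| True ratio | Raw and log(x+1) signs differ | Signs differ, at least one significant | Verdicts differ | Rejection, raw | Rejection, log |
|---|---|---|---|---|---|
| 1 | 18–26% | at most 0.1% | 5–6% | 4.3–5.0% | 5.0–5.2% |
| 0.85 | 12–24% | at most 0.3% | 11–13% | 7–14% | 11–21% |
| 0.75 | 6–18% | at most 0.6% | 19–25% | 13–32% | 26–53% |

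Two further sets of simulations assumed a 30% reduction and correlations between 0.4 and 0.7, one with gamma-Poisson counts and one with both count types. Verdicts differed in 11–25% and 13–33% of trials.

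**4. Type I error.** Each scale taken alone holds about 5%. Taking the smallest p-value of raw, square root and log gives 7.5–8% in the setting tabulated, and 6–10% across all the simulations. Choosing raw or log by a Shapiro test on baseline counts gave 4.2–5.5% in 16 settings, because skewed counts lead to the log almost every time.

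**5. The alternative.** Under randomisation mean b₁ and mean b₀ are equal in expectation, so the difference in mean 10-week value estimates the same quantity as the difference in mean change. Analysing the untransformed 10-week count with baseline adjustment held a null rate of 3.5–6.3%. With a 30% reduction it had more power than the planned raw change test in all 8 settings (for example 0.60 against 0.32) and more than the log change test in 7 of 8 (0.60 against 0.40; the exception was 0.56 against 0.59).

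**The case against.** The strongest reply is that this is ordinary under-specification, that a log is nowhere mentioned, and that a null treatment effect gives a null interaction on every scale. Most of that is right, and it limits what can be claimed.

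- A reader might infer that the plan converts its test into a comparison of ratios. It does not say so. Transformation is conditional, and only a log gives ratios.
- A reader might infer that the two scales would support opposite conclusions. Opposite signs are common, but nearly all occur among non-significant estimates near zero. With at least one scale significant they stayed under 1% of trials, and in the tabulated setting they never occurred with both significant.
- A reader might infer that the freedom to transform inflates false positives. It does so only if the scale is picked by its p-value. The plan describes a normality assessment, and such a rule held its level.
- A reader might infer that logging costs power. For the planned change test, log had more power than raw in every setting run. With baseline adjustment the order depends on the distribution: raw 0.48 against log 0.41 with gamma-Poisson counts, but 0.53 against 0.62 with lognormal counts.

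It is also fair to say that naming the scale for each outcome would be enough to close the gap. Most of the power gain in step 5 comes from baseline adjustment, not from avoiding the log.

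What the reply does not remove is the mismatch between a stated mean change and a test whose scale is settled later, or the frequency with which that choice changes the verdict when an effect exists.

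**Conclusion.** The point holds in limited form and should be fixed. The aim fixes a mean change; the analysis section permits an unnamed transformation that would replace it, for four of the six predicted measures. The practical consequence is a changed estimand and, with a true 30% reduction, a different significance verdict between raw and log in roughly 11–33% of trials. These figures rest on assumed gamma-Poisson or Poisson-lognormal counts, 40 analysed per arm and assumed correlations. The documents do not support a claim of reversed conclusions, of general type I error inflation, or of a power penalty from logging.

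**What to change.** For the drinking and consequence outcomes, remove the open-ended transformation and name one primary analysis before data are seen:

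- Compare the untransformed 10-week value between arms, adjusted for its baseline value, by either a log-link count model with arm and log(baseline + 1), or linear ANCOVA. Choose one now.
- Report the arm difference in mean drinks, days or consequences (by standardisation if the count model is used).
- Take the p-value from re-randomising arm labels, within wave if waves are used, or from another method valid in small samples. A Poisson model with robust standard errors had null rates of 5.2–7.0%.
- Give any transformed-scale analysis as sensitivity only, stating the transformation and how zeros are handled.
- Check that the count model suits outcomes bounded at 30 days or 24 items.

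The cost is a few lines of text and standard code. The downsides are a slightly less familiar model than ANOVA if the count model is chosen, and possibly some power lost against a log-scale analysis if the counts are close to lognormal.
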